Evaluation of the Efficacy of Procedural Sedoanalgesia and Infraclavicular Nerve Blockade on Analgesia in Forearm Fractures in the Emergency Department

1. Protocol

Trauma patients constitute a significant portion of emergency department visits. Forearm fractures are common upper extremity fractures in adult patients. A forearm fracture can present as an isolated radius fracture, an isolated ulna fracture, or a double bone radius-ulna fracture. Forearm fractures cause severe pain, both due to the fracture itself and during the reduction process. Pain management is crucial in emergency departments (ED). Therefore, multimodal approaches are available to reduce or eliminate pain during the reduction process. Procedural sedation and analgesia (PSA), which is widely used in emergency departments and effectively reduces pain, is particularly common. However, recent literature suggests the use of peripheral regional block techniques over the use of multiple nonsteroidal anti-inflammatory and/or opioid analgesics for pain palliation.

The aim of our study is to evaluate the success of reduction and pain palliation during the reduction process in patients with forearm fractures using PSA and ultrasound-guided infraclavicular nerve block (ICB). The secondary aim is to compare patient comfort, physician comfort, side effects, length of stay in the emergency department, and the need for pain medication after discharge between these two procedures, and to determine the most appropriate method. With this study, we aim to contribute to practical applications for achieving optimal pain control in patients with forearm fractures in emergency department settings.

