PSA (Procedural Sedation and Analgesia) refers to the suppression of a patient's consciousness to maintain vital heart and lung functions while using sedative and dissociative agents combined with analgesics during a medical procedure, with the goal of preventing or minimizing the patient's awareness, response, and memory of the event. However, the use of sedoanalgesic drugs carries significant risks, such as respiratory depression or hypotension, and requires that every patient be monitored and observed at least until they return to a presedation level of alertness. The need for the patient to stay in the emergency department for at least two hours and the requirement for staff to monitor the patient during this time present certain disadvantages, particularly in busy emergency departments. These concerns have led to the exploration of alternative approaches. Ultrasound (US)-guided peripheral nerve blocks are alternatives used in pain management during the reduction of forearm fractures. These techniques are widely used in outpatient settings, orthopedic surgeries, and postoperative pain management in operating rooms. Peripheral nerve blocks involve the use of local anesthetics and are defined as the infiltration of peripheral nerves with local anesthetic agents to reduce motor output and sensory input. Nerve blocks are effective in pain control, act quickly, have low complication rates, and do not require prolonged observation. As a result, the use of peripheral nerve blocks in pain management is increasing in emergency departments.

Patients presenting with forearm fractures to the emergency department will be included in the study. The need for reduction at the time of presentation will be determined by orthopedic doctors. Patients who require reduction and have an ASA classification of ASA 1-2 (ASA: American Society of Anesthesiologists, Table-1) will be included in the study and followed up. The patients will be randomly divided into two groups: Group P, where reduction will be performed under Procedural Sedation and Analgesia (PSA), and Group B, where reduction will be performed under ultrasound-guided infraclavicular nerve block (ICB). Randomization will be done by assigning the first 5 patients to Group P and the next 5 patients to Group B (the procedures are described in detail below), and the following parameters will be evaluated:

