Pain levels at the time of arrival, post-procedure but before reduction, and after reduction will be recorded using the Numeric Rating Scale (NRS). (NRS ranges from 0-10, with 0 representing no pain and 10 representing unbearable pain.)

The success of the reduction procedure will be assessed, noting whether additional reduction procedures were required, and the findings on control X-rays after each reduction (radial height, radial inclination, and volar tilt) will be recorded and evaluated by orthopedic doctors. The length of stay in the emergency department will be recorded as the time from the patient's arrival to discharge.

Side effects/complications during the procedures will be recorded.

The need for rescue treatment during the procedure will be evaluated. If the NRS is above 5, the first-line rescue analgesic treatment will be 50 or 100 mg of tramadol IV, administered in 100 cc of normal saline over 15 minutes. If the pain remains above NRS 5, the second-line

treatment will be 50 mcg of fentanyl IV, administered in 100 cc of normal saline over 15 minutes.

The need for pain medication within 24 hours after discharge will be assessed by calling the patients.

Patient satisfaction will be recorded using a 5-point Likert scale (1: very poor, 2: poor, 3: fair, 4: good, 5: very good).

The same satisfaction survey will be administered to the orthopedic doctors who performed the reduction.

Procedures for the groups will be as follows before reduction: The PSA protocol for Group P will be performed by experienced emergency physicians who are skilled in sedation analgesia, advanced life support, and advanced airway management. The patient will be monitored by an experienced doctor or nurse during the sedation period until recovery. Emergency equipment will be readily available in case of any complications. The PSA protocol will include IV ketamine administered at a dose of 1-2 mg/kg. If the NRS remains above 5, additional doses of 0.25-1 mg/kg may be repeated every 5 to 10 minutes as needed. The decision to discharge the patient will be based on the modified Aldrete score, one of the recovery scoring systems.

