The ultrasound (US)-guided infraclavicular nerve block protocol for Group B: The infraclavicular block (ICB) is a peripheral nerve block that anesthetizes the brachial plexus at the level of the cords. ICBs are used for anesthesia and/or analgesia during surgical or procedural interventions on the forearm, wrist, hand, and fingers. The block will be applied under ultrasound guidance as follows: The patient will be placed in a supine position, an intravenous (IV) line will be established, and the patient will be monitored. The patient's head will be turned to the side opposite the block site. The arm to be blocked will be adducted and placed in flexion across the patient's chest. After the block site is disinfected with povidoneiodine, a sterile linear ultrasound probe (the LOGIQ P9 ultrasound device currently used in our emergency department) will be placed longitudinally at the recommended site for the infraclavicular block . Once the axillary artery, vein, and the cords of the brachial plexus are visualized, a 22-gauge needle will be advanced in-plane with the ultrasound probe toward the 6-7 o'clock position relative to the artery. The lateral, medial, and posterior cords, containing hypoechoic nerve fascicles ("honeycomb" appearance), will be identified. First, 2 mL of saline will be injected; if the spread is appropriate, the local anesthetic (LA) solution, prepared by diluting 10 mL of 0.5% bupivacaine with 10 mL of normal saline to create 20 mL of 0.25% bupivacaine, will be injected in fractional doses with intermittent negative aspiration. The spread of the local anesthetic within the brachial plexus will be observed as an expanding hypoechoic collection within the plexus. Fifteen minutes after this procedure, the level of anesthesia will be assessed using a cold-hot test, and reduction and casting will be performed

Inclusion Criteria:

Age 18 years and older Diagnosed with a forearm fracture using standard radiography Hemodynamically stable No vascular or nerve injury No infection in the skin or tissues where the needle will pass Able to give written and verbal consent

Exclusion Criteria:

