Allergy to drugs used for sedation analgesia and peripheral nerve block Hemodynamically unstable Patients with ASA 3-4 classification (for those in the PSA group) Coagulopathy, liver or kidney failure Patients with opioid, alcohol, or substance abuse Skin infection or open wound at the site where local anesthetic will be applied Pregnant or suspected of being pregnant Those who do not give written and verbal consent

Sample Size: For the planned analyses in this study, the sample size calculation was based on the study by Tekin et al. titled 'Can ultrasound-guided infraclavicular block be an alternative option for forearm reduction in the emergency department? A prospective randomized study.' In that study, a 30% difference between the two groups was found to be significant, and thus, this article was used as a reference for our study. Based on this reference article, with an effect size of 0.5 (medium), an α level of 0.05, and a power of 0.80, it was determined that a total of 78 participants (39 in each group) would be sufficient. The sample size analysis was conducted using the GPower 3.1 program.

Volunteer recruitment for the study will be terminated once the total of 78 patients, as determined by the power analysis, is reached.

The study received approval from the Ankara Etlik City Hospital Ethics Committee on April 24, 2024 (approval code: AEŞH-EK1-2024-0040). However, patient recruitment has not yet started.

Volunteer Recruitment Start: September 1, 2024 [Expected] Primary Completion: June 1, 2025 [Expected] Study Completion: December 1, 2025 [Expected]

2. Statistical analysis

Statistical analysis will be performed using the SPSS 23.0 statistical software package. In the descriptive findings section, categorical variables will be presented as numbers and percentages, while continuous variables will be presented as mean \pm standard deviation for normally distributed data and as median (minimum, maximum) for non-normally distributed data. The normality of the distribution of continuous variables will be assessed using the Kolmogorov-Smirnov test. Comparisons between groups for categorical variables will be evaluated using the chi-square test. For normally distributed quantitative variables, comparisons between the three groups will be made using the ANOVA test. For non-normally distributed quantitative variables, the Kruskal-Wallis test will be used. A p-value of < 0.05 will be considered statistically significant in this study

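### Length of stay is timed from arrival and compared unadjusted, so waiting before inclusion adds variance that neither technique can change; one time stamp and a covariate would recover precision

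*Combined protocol and SAP*

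**What the plan says.** Section 1 (Protocol) lists length of stay among the secondary comparisons: the trial will "compare patient comfort, physician comfort, side effects, length of stay in the emergency department" and further outcomes between the two procedures. It defines the measure in one sentence: "The length of stay in the emergency department will be recorded as the time from the patient's arrival to discharge".

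Two steps come before a patient enters the trial. The Inclusion Criteria require that the patient be "Diagnosed with a forearm fracture using standard radiography". The protocol also says "The need for reduction at the time of presentation will be determined by orthopedic doctors", and only patients judged to need reduction are included and then assigned to a group.

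On assignment the protocol says: "Randomization will be done by assigning the first 5 patients to Group P and the next 5 patients to Group B".

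Section 2 (Statistical analysis) compares quantitative variables by ANOVA, or by Kruskal-Wallis if they are not normally distributed. It names no covariate for waiting time, run of assignment or calendar time. It refers to three groups, but the trial has two, so the check below treats the test as a two-group comparison. The documents specify no time stamp between arrival and discharge.

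**The concern.** Among the protocol's arguments for nerve block is that sedated patients need at least two hours in the department while blocked patients need no prolonged observation. That difference arises after the patient is in the trial. The measured interval adds time from before inclusion, which varies with how busy the department is and says nothing about technique. Under an unadjusted test this extra variation goes into the error term, so a real difference in stay is harder to detect and its confidence interval is wider.

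There is a secondary worry. Five consecutive patients share an arm, so a crowded spell could lengthen the waits of one arm more than the other. If no intermediate time is collected, neither problem can be repaired at the analysis stage.

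**Working it through.** **Inputs.** From Sample Size: 39 per group, α = 0.05, effect size 0.5. From the expected dates: 1 September 2024 to 1 June 2025 is 273 days for 78 patients. Not in the documents: any mean or SD for length of stay, or the share *s* of its variance due to waiting before inclusion. I assume *s* = 10%, 30% or 50%.

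**The plan's own figure.** The plan gives 78 patients "with an effect size of 0.5 (medium), an α level of 0.05, and a power of 0.80". For a two-sided comparison of two means, 39 per arm at d = 0.5 gives 58.7% power; 80% would need 64 per arm. So 78 does not follow from d = 0.5 for means. That is a separate point. The sample size was not tied to length of stay, and d = 0.5 serves here only as a reference effect.

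**Precision.** Write stay = W + T, with W the arrival-to-decision time and T the rest. If W and T are independent, removing W leaves a fraction 1 − s of the variance. The same difference in minutes then has standardised size d′ = 0.5/√(1 − s). Power comes from the noncentral t with 76 df and noncentrality d′√(39/2).

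| s | d′ | Noncentrality | Power |
|---|---|---|---|
| 0 (as planned) | 0.500 | 2.21 | 58.7% |
| 10% | 0.527 | 2.33 | 63.2% |
| 30% | 0.598 | 2.64 | 74.1% |
| 50% | 0.707 | 3.12 | 86.9% |

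The same loss can be read the other way. Let r = SD(W)/SD(T). Keeping W multiplies the required sample by 1 + r². An effect with 80% power on T alone falls to 70.7% at r = 0.5 and 50.8% at r = 1 (normal approximation).

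Independence matters. A positive correlation between W and T makes the loss larger; a sufficiently negative one could cancel it. Covariate adjustment estimates the slope instead of fixing it at one. Its gain depends on the squared correlation between stay and W, which equals s under independence, and it costs one degree of freedom.

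**Crowding.** The planned pace is 273/78 = 3.5 days per patient, so a run of five covers about 17 days (5 × 3.5 = 17.5). If the pattern repeats to 78, there are 16 runs, the last with three patients, giving 40 sedation and 38 block. I simulated this sequence with evenly spaced enrolment and no true effect. The correlation between successive waits was exp(−3.5/τ), where τ is how long crowding persists in days. Waiting made up 30% or 50% of the variance and was driven entirely by crowding, which is the worst case. False-positive rate of the nominal 5% t-test:

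| τ (days) | Correlation | Rate, rounded |
|---|---|---|
| 1 | 0.03 | 5% |
| 3 | 0.31 | 6% to 7% |
| 7 | 0.61 | 7% to 8% |
| 14 | 0.78 | 5% to 6% |
| 30 | 0.89 | 4% |

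If only half of the waiting variance is driven by crowding, the maximum is about 6.5%. Short-lived crowding is barely shared within a run. Slow drift is shared by neighbouring runs in opposite arms and largely cancels.

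**The case against.** Arrival-to-discharge is an unambiguous interval with an objective start, and it is what a department manages. The outcome is secondary. The power figures rest on variance shares that nobody has measured and on an effect size not chosen for this outcome. The low starting power of 59% mainly reflects 39 per arm being too few for d = 0.5. All of this stands. It limits the size of the point, but not the fact that the tested interval carries irrelevant variance.

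A reader might go further in three ways that the documents do not support.

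- *The false-positive rate is inflated to 6% to 12%.* That follows if runs are treated as independent clusters: intracluster correlation 0.1 × 0.3 = 0.03 to 0.3 × 0.5 = 0.15, design effect 1 + 4 × ICC = 1.12 to 1.60. But adjacent runs belong to opposite arms and share slow drift, and each run spans about 17 days. At the planned pace the top of that range is not reached.
- *The arrival clock biases the comparison.* The crowding risk comes from the predictable five-and-five assignment. Under random allocation the arrival clock would only add noise. Starting the clock later does not cure the assignment problem either, because crowding can also delay the control X-ray and discharge.
- *Timing should start at allocation.* The documents define no allocation event; the group follows from enrolment order, which staff can foresee. They do not say whether waiting for a sedation or block operator falls before or after allocation. Such a clock could be set differently by arm, or could discard delay that the technique itself causes.

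**Conclusion.** The point holds as a modest precision loss on a secondary outcome that a cheap change would reduce. Length of stay includes time before inclusion that the technique cannot alter, and the planned test does not adjust for it. At 39 per arm and d = 0.5, removing that time would lift power by about 4, 15 or 28 percentage points (from 58.7% to 63.2%, 74.1% or 86.9%) for assumed shares of 10%, 30% or 50%. These figures assume that waiting and later time are independent and that a t-type test is used. The documents cannot show which share applies.

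The crowding effect is secondary: about 4% to 8% false positives instead of 5%, under worst-case assumptions at the planned pace. It should be dealt with mainly under the allocation method. Nothing here shows that arrival-to-discharge is an invalid measure.

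**What to change.** 1. Record for every patient the clock time of the orthopaedic decision to reduce. It is a defined event before inclusion, so it is a firmer reference than an undefined allocation time. Because the assignment sequence is predictable, the plan should also say that the decision is made without regard to the next patient's group.
2. Keep arrival-to-discharge as the measure of stay. In section 2, replace the unadjusted test for this outcome with a comparison of the two groups adjusted for the arrival-to-decision interval, and state in advance the covariate-adjusted alternative to be used if stay is markedly skewed.
3. Report decision-to-discharge time by group alongside.

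The cost is one time stamp per patient and a covariate-adjusted model in place of a simple test for one secondary outcome. The document states that recruitment has not started, so on its own timeline the time could be collected from the first patient. This does not replace the need for properly random, concealed allocation.

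### Side effects are a between-arm comparison, but recording is tied to an undefined procedure window, so recovery-phase and post-discharge effects are not planned to be collected

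*Combined protocol and SAP*

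**What the plan says.** All the relevant text is in section 1, Protocol, of the combined protocol and SAP.

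- **Aim.** The aims paragraph makes side effects a comparison between the arms: "The secondary aim is to compare patient comfort, physician comfort, side effects, length of stay in the emergency department". The list ends with the goal of identifying the better-suited method.
- **Collection rule.** The list of outcome measures has one sentence on the subject: "Side effects/complications during the procedures will be recorded". It gives no end time, event list or assessor.
- **Group P.** The sedation paragraph names an observer and an end point: "The patient will be monitored by an experienced doctor or nurse during the sedation period until recovery". It then adds "The decision to discharge the patient will be based on the modified Aldrete score, one of the recovery scoring systems".
- **Group B.** The block paragraph says "an intravenous (IV) line will be established, and the patient will be monitored". Its last timed step is "Fifteen minutes after this procedure, the level of anesthesia will be assessed using a cold-hot test", followed by reduction and casting. It gives no observer, duration or recovery end point.
- **Background on sedation.** The protocol says that sedation "requires that every patient be monitored and observed at least until they return to a presedation level of alertness".
- **After discharge.** "The need for pain medication within 24 hours after discharge will be assessed by calling the patients". No side-effect enquiry is specified for that contact.

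Section 2, Statistical analysis, assigns the chi-square test to categorical variables and makes no allowance for differing lengths of observation.

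**The concern.** A side-effect comparison needs the same window, the same questions and the same intensity of enquiry in both arms. Here the window is tied to a word that the protocol uses in two ways, and nothing says whether recovery lies inside it. The protocol's own background places sedation risk in the period up to the return of alertness, yet the recording rule does not clearly reach that far. On the block side, reduction and casting are done while the block is working, so any effect that appears later also falls outside a strictly read window.

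At stake is a stated secondary comparison that contributes to the choice between methods. A count that stops too early understates harm in both arms. A count that stops at different times in the two arms could also distort the difference between them.

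**Working it through.** The plan gives no side-effect rate and no figure on this point, so there is nothing to reproduce. The check is a reading of the text, followed by a labelled illustration.

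**Step 1: what procedure means.** The pain-score schedule places one measurement after the procedure and ahead of reduction, so there the word means the sedation or block. The next sentence, on success, applies it to the reduction. The aims paragraph calls the two techniques procedures. No definition settles it.

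**Step 2: where each reading closes the window.**

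| Reading | Window closes | Recovery effects | Post-discharge effects | Same in both arms? |
|---|---|---|---|---|
| Sedation or block only | Before reduction | Not planned | Not planned | Nominally yes |
| Through reduction and casting | At casting | Not planned | Not planned | Nominally yes |
| Includes Group P's sedation period to recovery | Group P: at recovery. Group B: not stated | Planned in Group P, unclear in Group B | Not planned | Not assured |

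No reading gives a comparison that is both complete and assured to be equal. The first two need no inference beyond the recording sentence. The third adds possible unequal capture.

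**Step 3: illustration of unequal capture under the third reading.** Inputs:

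- n = 39 per arm, from the Sample Size paragraph.
- True risk r, the same in both arms: assumed 20%, then 10%.
- Share captured c: assumed 1 in Group P, and 0.75, 0.50 or 0.25 in Group B.

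Formulas: observed rate = r × c; expected patients = 39 × r × c.

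| r | Group P | Group B, c = 0.75 | Group B, c = 0.50 | Group B, c = 0.25 |
|---|---|---|---|---|
| 20% | 20% (7.8) | 15% (5.9) | 10% (3.9) | 5% (2.0) |
| 10% | 10% (3.9) | 7.5% (2.9) | 5% (2.0) | 2.5% (1.0) |

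The spurious difference is 5 to 15 points at a 20% risk and 2.5 to 7.5 points at a 10% risk.

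**Step 4: would the planned test react?** For 8 of 39 versus 4 of 39, uncorrected chi-square = 78 × (8 × 35 − 4 × 31)² / (39 × 39 × 12 × 66) = 1.58, p about 0.21. For 8 versus 2, near the extreme of the range, p is about 0.04 uncorrected and 0.09 by Fisher's exact test. In the central case the distortion would sit in the estimate and would not produce a significant result.

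**The case against.** The strongest reply is that the recording sentence stands ahead of the group-specific text and applies equally to both arms. The Group P sentence describes patient care, not data capture. Group B is also monitored. Both arms have contact after reduction: a pain score, control X-rays, and length of stay timed to discharge. No script for the telephone call is given, so one cannot say that it excludes side effects. The background describes blocks as having few complications and needing only short observation, and the documents give neither a duration for bupivacaine nor any late block complication.

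Most of this stands, and it rules out a stronger reading. A reader might infer that the side-effect comparison is biased in favour of the block, that Group B goes unobserved after casting, or that late block effects will certainly be lost. The documents do not establish any of these. Silence about an end point is not a statement that monitoring stops. If the window is applied strictly in both arms, most of the directional bias disappears. The illustration rests wholly on assumed rates and capture shares.

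The reply does not remove the narrower point. Equal windows that both close at or before casting still leave recovery and post-discharge effects outside the plan. Contact after reduction is not a side-effect enquiry unless the protocol makes it one.

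**Conclusion.** The point holds in a limited form. As written, the plan does not provide for collecting side effects that arise in recovery or after discharge, in either arm, on a strict reading of its only collection rule. That conclusion rests on the text alone.

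Unequal capture is possible, not shown. It depends on two assumptions: that the sedation period up to recovery is treated as part of the procedure in Group P, and that Group B has no equivalent enquiry in practice. If both hold, the error would tend to favour the block. Its size cannot be derived from the documents; 20% versus 10%, or 10% versus 5%, shows the mechanism only.

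This should be corrected, but it does not bear on the main aim of pain relief and reduction success. Side effects are one of five secondary comparisons.

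**What to change.** Replace the recording sentence with one window for both arms: from the start of sedation or block to the existing telephone call at about 24 hours after discharge. Then:

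1. Use one checklist, identical in both arms, at discharge from the emergency department and again at the call. Name who completes it.
2. Compare the arms on this common window.
3. Report events up to the end of reduction and casting as a defined subset, so that the term procedure no longer carries the definition.
4. Record the time of the call. The window is tied to discharge, so its length will vary somewhat with time spent in the department.

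This concerns outcome recording only. It changes no monitoring or discharge rule, and no sample size.

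The cost is a reworded sentence, a short form and a few more minutes in a call already planned. Reported rates will be higher, and some late events will rest on patient recall. A common checklist does not remove the difference in who watches the patient before discharge, so that limit should be acknowledged in the report. The protocol states that recruitment had not begun; if that is still so, the change can apply to every participant.

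### The ASA eligibility rule differs between the population paragraph and the Exclusion Criteria, and as listed it applies to one arm only

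*Combined protocol and SAP*

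**What the plan says.** Section 1 (Protocol) deals with ASA class in two places.

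- **Study population paragraph.** "Patients who require reduction and have an ASA classification of ASA 1-2" are to be included and followed up. Allocation is described only after this: "The patients will be randomly divided into two groups: Group P, where reduction will be performed under Procedural Sedation and Analgesia (PSA), and Group B", the latter receiving the infraclavicular block. The method is then given: "Randomization will be done by assigning the first 5 patients to Group P and the next 5 patients to Group B".
- **Exclusion Criteria.** The list bars "Patients with ASA 3-4 classification (for those in the PSA group", closing the parenthesis there.

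The Inclusion Criteria, which begin "Age 18 years and older Diagnosed with a forearm fracture using standard radiography Hemodynamically stable", contain no ASA item.

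Section 2 (Statistical analysis) plans unadjusted comparisons. For example, "Comparisons between groups for categorical variables will be evaluated using the chi-square test"; ANOVA or Kruskal-Wallis is planned for quantitative variables.

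**The concern.** In a two-arm comparison, eligibility should be settled before assignment and be the same for both arms. An exclusion defined by group membership breaks this: it can be applied only if the arm is already known when eligibility is judged. Here the arm would be known, because patients are assigned in fixed runs of five.

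Staff who follow the two lists exactly could therefore turn away an ASA 3-4 patient during a Group P run and accept the same patient during a Group B run. Group B could then include higher-ASA patients while Group P had none. The outcomes most exposed are secondary ones named in the aims, such as side effects and length of stay in the emergency department. ASA class is not among the parameters that section 1 lists for recording, so an imbalance might not be visible in the report.

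**Working it through.** The plan states no figure to reproduce on this point. The check is a comparison of texts, followed by a count of what the literal reading would allow.

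**1. The texts side by side**

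| Place in section 1 | ASA rule | Applies to |
|---|---|---|
| Study population paragraph | ASA 1-2 required | All patients, before division into groups |
| Inclusion Criteria | None | – |
| Exclusion Criteria | ASA 3-4 excluded | Group P only, as written |

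**2. Item counts**

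- The Inclusion Criteria have 6 items: age, radiographic fracture, haemodynamic stability, no vascular or nerve injury, no infection along the needle path, and consent. Items mentioning ASA: 0.
- The Exclusion Criteria have 8 items: drug allergy, instability, ASA class, coagulopathy or liver or kidney failure, substance abuse, skin infection or wound, pregnancy, and no consent. Items that name an arm: 1, the ASA item.
- The drug-allergy item covers the drugs of both techniques for everyone. The block-site item, "Skin infection or open wound at the site where local anesthetic will be applied", also names no arm. A reader could reasonably take the ASA qualifier as deliberate.

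**3. Two ways of applying the rules to an ASA 3-4 patient**

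- Population paragraph and lists together: not eligible for either group. Expected ASA 3-4 patients: 0 in P and 0 in B.
- Lists alone: not eligible in a Group P run; not barred by ASA class in a Group B run.

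**4. Enrolment positions affected under the lists-alone reading**

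This assumes that runs of 5 P then 5 B repeat until 78 patients are enrolled.

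- Full cycles of 10 in 78: 7, giving 70 patients (7 × 5 = 35 P and 35 B).
- Remaining 78 − 70 = 8 patients: 5 P and 3 B.
- Totals: 35 + 5 = 40 P and 35 + 3 = 38 B. The Sample Size paragraph states 39 and 39.

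So 38 positions would be open to ASA 3-4 patients and 40 closed.

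**5. Conversion to patients**

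Let q be the ASA 3-4 share among otherwise eligible patients. The documents give no value, so q is an assumption. The expected number in Group B is q × n; in Group P it is 0.

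| Assumed q | Group B, n = 38 | Group B, n = 39 (planned size) | Group P |
|---|---|---|---|
| 5% | 1.90 | 1.95 | 0 |
| 10% | 3.80 | 3.90 | 0 |
| 20% | 7.60 | 7.80 | 0 |

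The exclusions common to both arms (instability, coagulopathy, liver or kidney failure, substance abuse) would remove some ASA 3-4 patients, so q refers to those who remain. The table converts a share into a count. It is not evidence of how large the imbalance would be.

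**The case against.** The strongest reply is that eligibility conditions are normally cumulative. The population paragraph admits only ASA 1-2, nothing states that ASA 3-4 patients may enter Group B, and the exclusion item is then redundant, narrower wording. The lists are also visibly incomplete on their own: the need for reduction, which defines the study population, appears in the population paragraph and in neither list. They have to be read with that paragraph. This is good evidence that the lists-alone reading is not the intended one, and it lowers the likelihood of harm. It does not show that staff screening from the lists would consult both, and the documents do not say which text prevails.

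Three further objections stand in part:

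- **The contrast with the skin item is debatable.** The Group P procedure described uses no local anaesthetic, so that item may limit itself to the block arm by its own terms. The contrast is only supporting detail; the conflict between the two ASA statements does not depend on it.
- **The 40 and 38 split is conditional.** The protocol describes only the first two runs of five, and the Sample Size paragraph gives 39 per group. Using 39 makes no material difference.
- **Predictable allocation is a separate defect.** It should not be counted again here. It matters to this point only because it makes an arm-specific exclusion workable in practice.

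**Conclusion.** The concern holds. The mismatch between the population paragraph and the Exclusion Criteria is certain from the text; its consequence is conditional. If the population paragraph is applied to everyone, the effect is zero and what remains is a wording error. If the lists are used alone, ASA class can differ between arms by rule, and the planned tests make no adjustment for it. The size of any resulting bias cannot be determined, since it depends on an ASA 3-4 share that the documents do not give. The exposure is in secondary outcomes such as side effects and length of stay; no effect on procedural pain or reduction success is claimed. The correction should be made because it is nearly free and removes an arm-dependent eligibility rule.

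**What to change.** Reconcile the study population paragraph, the Inclusion Criteria and the Exclusion Criteria into one ASA criterion, worded identically wherever it appears and applied to both groups. The investigators decide the limit. Deleting the arm-specific qualifier is the smallest edit that agrees with the population paragraph; if a different limit is chosen, that paragraph must be amended too.

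Confirm and record ASA class, with all other eligibility criteria, before the patient is assigned, and report ASA class by group at baseline.

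The cost is a wording edit and one line on the screening form. The protocol says of its own status "However, patient recruitment has not yet started", so under this version the change can be made before the first patient. If the population paragraph's limit is kept, ASA 3-4 patients who might have entered the block arm are not enrolled, which that paragraph already requires.

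This edit does not provide allocation concealment. The runs of five would still reveal the next arm, and that needs a separate change to the allocation method.
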